- Urine pregnancy test (for females of childbearing potential)

Subjects will receive a pretreatment regimen for infusion reaction prophylaxis. The regimen is as follows:

- Dexamethasone 10 mg PO 24-18 hours prior to administration of study drug.
- Acetaminophen 1000 mg PO 1 hour prior to administration of study drug.
- Either loratedine 10 mg PO or cetirizine 10 mg PO one hour prior to the administration of study drug.

In the event that dexamethasone was not administered previously, then 10 mg dexamethasone IV may be administered 1-3 hours prior to study drug administration.

Following completion of pre-dose assessments and administration of pretreatment regimen according to the appropriate timelines above, study drug will be administered by IV infusion over 30 minutes.

Subjects will remain in the clinic for up to 4 hours following completion of the 30 minutes IV infusion for PK assessment and safety follow-up. The following procedures will be conducted post-dose:

- Vital signs: 15 minutes (during infusion), 30 (+ 15) minutes (immediately post-infusion), 2 hr (±20 minutes) and 4 hr (±20 minutes) following initiation of study drug infusion.
- ECG at 30 (+15) minutes after initiation of study drug infusion.
- Blood samples for bertilimumab (PK analysis) at 30 (+15) minutes (immediately post-infusion) and 4 hours (±20 minutes) following initiation of study drug infusion.
- Recording of AEs (including post-infusion reactions, if applicable) and concomitant medications.

5.3 FOLLOW-UP PERIOD¹: VISIT 5 (DAY 35), VISIT 6 (DAY 42), VISIT 7 (DAY 56) AND VISIT 8 (DAY 90)

Subjects will be followed for 3 months post first study drug administration. The following assessments will be performed at the follow-up visits:

- Physical exam
- Vital signs
- ECG
- AE and concomitant medication recording
- Partial Mayo score (at Visits 5, 6 and 8)
- Safety laboratory evaluations: hematology, biochemistry, antibodies to bertilimumab
- Blood samples for eosinophil count, serum eotaxin-1ⁱ, hs-CRP^j and ECP
- Blood samples for bertilimumab (PK analysis)
- Calprotectin in fecal samples
- Flexible sigmoidoscopy with biopsies. On Day 56 (or early discontinuation visit), at least 3 tissue samples are required from the same region where the Screening

¹ Visits during the Follow-Up Period have a ±3 day window.

biopsies were obtained. Additional biopsy samples may be obtained at the Investigator's discretion for histological assessment.

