6.9.1 Allowed Medications

The following concomitant medications/therapies will be allowed during the treatment period:

- Occasional use of NSAID and acetaminophen for headache, arthritis, myalgia, menstrual cramps etc., and daily use of low-dose (81-162 mg) aspirin for cardiovascular prophylaxis is permitted
- Mesalazine ≤ 4.8 g is allowed if the dose during the 2 weeks prior to the screening visit was stable; subject is to remain on stable dose through Visit 6 (Study Day 42).
- Systemic corticosteroids not exceeding the equivalent of 20 mg/day of prednisone (see Corticosteroid Comparison Chart below) are allowed if the dose during the 4 weeks prior to the screening visit was stable; subject is to remain on stable dose through Visit 6 (Study Day 42), excluding corticosteroid used in pretreatment prophylaxis.

• Cortiment (budesonide) up to a daily dose of 9 mg is allowed during the screening period and throughout the study owing to limited systemic absorption.

Table 1: Corticosteroid Comparison Chart

	Approximate Equivalent Dose, mg	Relative Potency
Hydrocortisone	20	1.0
Cortisone Acetate	25	8.0
Prednisone	5	4.0
Prednisolone	5	4.0
Methylprednisolone	4	5.0
Dexamethasone	0.75	30-150

Reference: Welsh GA, Manzullo EF and Nieman LK. The surgical patient taking glucocorticoids. 2007 UpToDate® www.uptodate.com.

Additional medications/therapies may be allowed at the discretion of the Investigator in consultation with the Sponsor. All concomitant medications used to treat AEs will be recorded in the subject's medical file and on the appropriate CRF page.

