## 6 Analysis Populations

## **6.1 Safety Analysis Population**

The Safety Analysis Set will include all subjects who were exposed to any of the study treatments (bertilimumab or placebo; i.e. that drug administration data has been collected) and/or prophylactic treatment where applicable (i.e. prophylactic premedication form is completed or prophylactic pre-treatment medication was used, as per the concomitant medication form).

It should be noted that the requirement of prophylactic medications was added as part of the protocol version 8 amendment and, therefore, this information is not available for all subjects in the study.

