#### **General Infusion Reaction (CRF Injection Site Reaction Assessment)**

• Frequency distribution of Skin Tolerability by visit, time point and treatment group.

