## 9.4.4 Pharmacodynamics (PD)

• Descriptive statistics of PD parameters as described in section 7.5 by visit, time point and treatment group.

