## 9.4.5 Covariate Analysis

The primary and secondary analysis will be conducted on the mITT population, and examine the following covariates:

Age

- Gender
- Prior TNF treatment
- Screening total Mayo score
- Screening UCEIS total score
- Screening tissue Eotaxin-1 levels
- Screening tissue Eosinophil count
- Baseline fecal calprotectin levels (visit 2)
- Baseline Hs-CRP (visit 2)
- Combined Site

For each of the listed above covariates descriptive statistics of primary endpoint/s by covariate levels will be presented. Continuous covariates will be divided into quartiles for this presentation.

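### Infusion-reaction and Day 0-based blood PD tables pool premedicated and unpremedicated subjects in a mix that the SAP never reports

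*SAP*

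**What the plan says.** **Premedication came in part-way.** The Protocol Version History places it under version 8.0 and gives prevention of infusion reactions as its purpose. Protocol Section 5.2 sets out the regimen, including "Dexamethasone 10 mg PO 24-18 hours prior to administration of study drug". SAP Section 6.1 records that "the requirement of prophylactic medications was added as part of the protocol version 8 amendment" and that "this information is not available for all subjects in the study". It accepts two sources of evidence for premedication: the premedication form, or that "prophylactic pre-treatment medication was used, as per the concomitant medication form". SAP Section 1.2, by contrast, describes premedication as if every subject received it.

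**The tables do not use it.** Under General Infusion Reaction, SAP Section 9.3 plans "Frequency distribution of Skin Tolerability by visit, time point and treatment group". SAP Section 9.4.4 plans "Descriptive statistics of PD parameters as described in section 7.5 by visit, time point and treatment group". SAP Section 9.4.5 begins "The primary and secondary analysis will be conducted on the mITT population, and examine the following covariates" and lists ten covariates. None is premedication or protocol version, and the section presents the primary endpoint by covariate level, not safety or PD.

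**Listings.** SAP Sections 9.3 and 10 provide by-subject listings of adverse events, of past and concomitant medication with dates and times, and of all CRF data.

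**The concern.** Infusion reactions are a named safety endpoint, and Protocol Section 1.3.2 reports three earlier reactions with bertilimumab, one of them serious. Premedication is the measure intended to change that rate. If it was given to some subjects and not others, the rate in an arm depends partly on how many of its infusions came before the amendment took effect. A reader using the rate to plan the next study could not tell which regimen it reflects.

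Blood PD raises a separate question. Blood eosinophils, serum eotaxin-1 and hs-CRP are measured as change from a Day 0 pre-dose sample. In a subject premedicated by mouth, that sample is drawn after dexamethasone. In an unpremedicated subject it is not. The same change score then has a different starting point in the two groups.

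**Working it through.** The plan states no figure on this point to reproduce. The check is of the text, with supporting arithmetic.

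**1. Is the regimen change material by the protocol's own standard?** Protocol Section 6.9.1, Table 1, equates dexamethasone 0.75 mg with prednisone 5 mg.

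- 10 mg dexamethasone = 10 / 0.75 × 5 = 66.7 mg prednisone-equivalent.
- The same section allows "Systemic corticosteroids not exceeding the equivalent of 20 mg/day of prednisone" as background treatment and exempts premedication from the stable-dose rule. The ratio is 66.7 / 20 = 3.3.

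**2. What does pooling do to a within-arm reaction rate?** Let w be the unpremedicated share, p0 the rate without premedication and p1 the rate with it. The pooled rate is w·p0 + (1 − w)·p1. The documents give none of these, so all are assumed, with p1 = 5%:

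| w | p0 = 10% | ratio to p1 | p0 = 15% | ratio to p1 |
|---|---|---|---|---|
| 25% | 6.25% | 1.25 | 7.5% | 1.5 |
| 50% | 7.5% | 1.5 | 10.0% | 2.0 |
| 75% | 8.75% | 1.75 | 12.5% | 2.5 |

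As w approaches 0 the ratio approaches 1.

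**3. What does pooling do to blood PD?** Suppose oral dexamethasone shifts a marker by δ at the time of a pre-dose sample and the shift has gone by Day 35, seven days after the last planned infusion. With B and T the values that would be seen without dexamethasone at Day 0 and at the later visit:

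- Unpremedicated change: T − B.
- Premedicated change at Days 35 to 90: T − (B + δ) = (T − B) − δ.
- Premedicated change at Days 14 and 28: (T + δ) − (B + δ) = T − B, if δ is constant.
- Pooled mean change at Days 35 to 90: (T − B) − (1 − w)·δ.

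The pooled value depends on w, and the dependence differs by visit. Neither δ nor its sign is in the documents; that dexamethasone moves these markers at all is an assumption. For subjects given the intravenous alternative one to three hours before infusion, Protocol Section 5.2 does not fix whether the blood sample comes before or after it.

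**4. Which PD endpoints are exposed?** Tissue eotaxin-1 and eosinophils run from Screening, before any premedication, to Day 56, which is 56 − 28 = 28 days after the last planned infusion. ECP entered in version 8, so its data should come mainly from subjects treated under that version, unless stored samples were assayed. That leaves the blood markers measured from Day 0.

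**5. Does the planned infusion-reaction table measure infusion reactions?** The SAP heading ties it to the CRF Injection Site Reaction Assessment, and its content is skin tolerability. Version 8 withdrew that assessment and substituted graded infusion reactions (Appendix D). The SAP has no table of Appendix D grades. The instrument and the regimen changed in the same amendment, so splitting the existing table would not show reactions by regimen.

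**6. Denominator.** SAP Section 6.1 admits subjects with premedication and no infusion to the safety set. Protocol Section 8.3.1.1 counts only exposure to study treatment. A subject never infused cannot have an infusion reaction.

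**7. What precision would a split leave?** At full enrolment, 42 subjects at 2:1 give 28 and 14. With zero events, the exact 95% upper bound is 1 − 0.025^(1/n):

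| n | Group | Upper bound |
|---|---|---|
| 28 | active, pooled | 12.3% |
| 14 | active half, or placebo pooled | 23.2% |
| 7 | placebo half | 41.0% |

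**The case against.** Much of the case on the other side stands.

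- **The arms are comparable.** Both arms receive premedication under version 8, and blocks are assigned in sequence within the anti-TNF strata, so the mix should be similar across arms apart from chance. A reader might infer a biased treatment comparison; the design does not support that.
- **The pre-amendment number is unknown.** A reader might infer that the tables describe neither regimen. If few subjects preceded version 8, the pooled table nearly describes the premedicated regimen.
- **The ratios come from assumed rates.** A reader might take 1.25 to 2.5 as an estimate of error. It is only an illustration.
- **Not all PD is affected.** Tissue PD and ECP are little exposed, as shown above.
- **The information is not lost.** With at most 42 subjects, individual reactions can be matched to recorded premedication through the listings.
- **The covariate section is not the cause.** Adding premedication to SAP Section 9.4.5 would give clinical response by premedication. It would leave the safety and PD tables unchanged.
- **Precision is poor,** and the study is exploratory and descriptive.

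These points narrow the concern without removing it. Listings let a diligent reader reconstruct the mix, but no summary states it. Small cells limit inference; they do not prevent a descriptive table from saying which regimen its subjects received.

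**Conclusion.** The concern holds in a limited form. SAP Sections 9.3 and 9.4.4 combine subjects treated with and without premedication. The within-arm infusion-reaction rates and the Day 0-based changes in blood PD markers therefore reflect an undisclosed mix of two regimens. By the protocol's own conversion, the regimens differ by 66.7 mg prednisone-equivalent before each infusion.

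The effect on interpretation cannot be sized from the documents, because neither the unpremedicated count, the reaction rates nor the response of the blood markers to dexamethasone is given. The problem concerns the meaning of absolute rates and changes, not the validity of the randomized comparison. The missing table of Appendix D grades belongs to the same repair, since without it the SAP does not summarize the infusion reactions that version 8 collects.

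**What to change.** Amend SAP Sections 9.3 and 9.4.4, before unblinding if that is still possible:

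1. Report, by arm, the number of subjects and of infusions with premedication, without it, and with status unknown, using the premedication and concomitant-medication forms. Do not treat a missing form as no premedication. Count per infusion, since a subject could have been part-way through treatment when version 8 took effect.
2. Present infusion reactions by premedication actually received before that infusion, within arm, and keep the pooled column.
3. Present blood PD changes from Day 0 by premedication received before the Day 0 infusion, noting oral or intravenous dexamethasone, and keep the pooled column.
4. Tabulate infusion reactions by Appendix D grade where collected, with infused subjects as the denominator. Keep the skin-tolerability table for subjects assessed on that form, labelled as such.

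The cost is SAP wording and a few extra tables from sources that SAP Section 6.1 already names. The downside is small cells: about 14 per active subgroup if 28 active subjects split evenly, and 7 per placebo subgroup. The tables should be labelled descriptive, with no test between premedication groups.

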## **6.2 Efficacy Analysis Populations**

#### **6.2.1** Modified Intent to Treat (mITT)

The modified intent to treat (mITT) analysis set will include all randomized subjects who received at least one dose of study treatment (placebo or bertilimumab) (i.e. "Date of Drug Administration" is not missing), and had a full Mayo score (i.e. all 4 sub-scores completed) at screening and at least one post-baseline full Mayo score (see Section 8). Subjects with major entry violations as determined by blind review will be excluded from this population.

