8.3.1.2 Modified Intent to Treat Analysis Set

The modified intent to treat (mITT) analysis set will include all randomized subjects who received at least one dose of study treatment (placebo or bertilimumab), and had at least a full Mayo score at screening and at least one post-baseline partial Mayo score from visit 3 onward. Excluded from mITT will be subjects with major entry violations as determined by blind review.

Missing primary efficacy data in mITT will be imputed as follows:

Full Mayo Score at Visit 7:

- Subjects with a Full Mayo Score post-screening prior to Visit 7 (and none at Visit 7) will have their Visit 7 score imputed by last observation carried forward (LOCF).
- Subjects with a Full Mayo Score after Visit 7 (and none at Visit 7) will have their Visit 7 score imputed by last observation carried backward (LOCB).
- Subjects with only partial Mayo score(s) from Visit 3 onward will have their Full Mayo Score at Visit 7 imputed by multiple imputation (MI), using a model that includes screening data, treatment and partial Mayo Score.ⁿ

UCEIS (a secondary endpoint that will be analyzed in mITT as well)

Protocol: Immune/BRT/UC-01 Page 39 of 58 Final Version 8.0 May 23, 2018

ⁿ a) The continuous Full Mayo Score will be imputed using MI, after which clinical response will be computed and b) Should there be variables causing the MI model not to converge, these will be excluded from the model.

- Subjects with UCEIS post-screening prior to Visit 7 (and none at Visit 7) will have their Visit 7 score imputed by last observation carried forward (LOCF).
- Subjects with UCEIS after Visit 7 (and none at Visit 7) will have their Visit 7 score imputed by last observation carried backward (LOCB).
- Subjects with no post-screening endoscopy will have their UCEIS at Visit 7 imputed by MI using screening data, treatment and partial Mayo Score (from Visit 3 onward).^o

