# **List of Abbreviations**

	,	
AE	Adverse Event	
CRF	Case Report Form	
CS	Clinically Significant	
FAS	Full Analysis Set	
IV	Intravenous Infusion	
LOCB	Last Observation Carried Backward	
LOCF	Last Observation Carried Forward	
MI	MI Multiple Imputation	
mITT	mITT Modified Intent to Treat	
NCS	CS Non-Clinically Significant	
PD	Pharmacodynamics	
PK	Pharmacokinetics	
PO	Per Os	
PP	Per Protocol	
PPD	Purified Protein Derivative	
SAE	Serious Adverse Event	
SAP	SAP Statistical Analysis Plan	
SOC	OC System Organ Class	
ТВ	Tuberculosis	
TEAE	Treatment-Emergent Adverse Event	
TNF	Tumor Necrosis Factor	
UC	Ulcerative Colitis	
UCEIS	Ulcerative Colitis Endoscopic Index of Severity	

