#### Full Mayo Score at Visit 7:

- Subjects with missing Mayo Score at visit 7 will be imputed with the post-screening Full Mayo Score (obtained from early discontinuation or unscheduled visit) according to the date which is most close to visit 7's date of that subject. In other words, visit 7 score will be imputed by last observation carried forward (LOCF) or last observation carried backward (LOCB) depending on the date of the score. Note: Imputation will be done only if the score date is no more than ± 4 weeks from Visit 7 date.
- In the case there is non-trivial amount of missing data sensitivity analyses will be explored.

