#### UCEIS (a secondary endpoint that will be analyzed in mITT as well)

- Subjects with missing UCEIS Score at visit 7 will be imputed with the post-screening UCEIS Score (obtained from early discontinuation or unscheduled visit) according to the date which is most close to visit 7's date of that subject. In other words, visit 7 score will be imputed by last observation carried forward (LOCF) or last observation carried backward (LOCB) depending on the date of the score. Note: Imputation will be done only if the score date is no more than ± 4 weeks from Visit 7 date.
- In the case there is non-trivial amount of missing data sensitivity analyses will be explored.

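### The SAP requires a post-baseline full Mayo score for mITT where the protocol accepts a partial one, drops the protocol's multiple imputation and adds a ±4-week carry limit, with no reason given

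*SAP*

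**What the plan says.** **Entry to mITT.** Protocol 8.3.1.2 takes randomized, dosed subjects who "had at least a full Mayo score at screening and at least one post-baseline partial Mayo score from visit 3 onward". SAP 6.2.1 takes those who "had a full Mayo score (i.e. all 4 sub-scores completed) at screening and at least one post-baseline full Mayo score". Four completed sub-scores include the endoscopic one, so the SAP rule needs a post-dose endoscopy. Both documents also exclude major entry violations found at blind review.

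**Missing Visit 7 Mayo.** The protocol carries an available full score forward or backward with no time limit. Where none exists it says: "Subjects with only partial Mayo score(s) from Visit 3 onward will have their Full Mayo Score at Visit 7 imputed by multiple imputation (MI"), with screening data, treatment and partial Mayo in the model. The SAP keeps only the carrying, taken from an early discontinuation or unscheduled visit, and adds: "Imputation will be done only if the score date is no more than ± 4 weeks from Visit 7 date".

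**Missing Visit 7 UCEIS.** The protocol says: "Subjects with no post-screening endoscopy will have their UCEIS at Visit 7 imputed by MI using screening data, treatment and partial Mayo Score". The SAP says: "Subjects with missing UCEIS Score at visit 7 will be imputed with the post-screening UCEIS Score", under the same ±4-week limit and without MI.

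**What remains in the SAP.** "In the case there is non-trivial amount of missing data sensitivity analyses will be explored". The entry "MI Multiple Imputation" stands in the abbreviation list, but MI is used nowhere in the body. The table of contents lists no section on changes from the protocol, and 6.2.1 gives no reason.

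**The concern.** The SAP changes who is in the primary efficacy set and removes a prescribed imputation, so the two documents define different primary analyses. Under the SAP, a subject is excluded because the outcome is missing. Protocol 4.5 lists reasons for withdrawal that can relate to treatment or outcome: grade 3 or 4 infusion reactions, need for prohibited medication, and progression or relapse. Exclusion linked to such reasons can bias the responder proportions in either direction.

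Data already collected are also set aside. Partial Mayo scores are scheduled at each visit from Day 0 and need no endoscopy, yet an excluded subject's scores would appear only in the listings (SAP 10).

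**Working it through.** The plan states no figure for this point. The check compares the texts and then sizes the effect.

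**1. Which analyses lose the subject.** The primary analysis uses mITT (SAP 9.4.1), the secondary analyses use mITT and PP (9.4.2), and the covariate analysis uses mITT (9.4.5). PP is a subset of mITT (6.2.2). A dosed subject with partial scores from Visit 3 but no post-dose full Mayo is therefore in none of them. PK and PD (9.4.3, 9.4.4) name no analysis set, so nothing follows for them.

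**2. The sets are not nested.** The SAP has no visit floor. It keeps a subject withdrawn before Visit 3 who has a post-dose full Mayo, whom the protocol's Visit 3 condition can leave out. It loses the subject with partial scores only, whom the protocol keeps.

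**3. Size per subject.** Up to 42 subjects at 2:1 gives 28 active and 14 placebo.
- One unknown outcome: 1/28 = 3.6 points (active); 1/14 = 7.1 points (placebo).
- Assumed 0 to 2 per arm (not from the documents): 0 to 2/28 = 7.1 points active, 0 to 2/14 = 14.3 points placebo, and 0 to 21.4 points for the difference. These are worst-case widths, not estimates of bias.
- Direction, assuming 14/28 true active responders and two subjects excluded: if both are non-responders the rate reads 14/26 = 53.8%; if both are responders it reads 12/26 = 46.2%.

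**4. The carry limit.** Around planned Day 56, ±28 days covers Day 28 to Day 84.
- Visit 3 window, Day 12 to 16: 56 − 16 = 40 to 56 − 12 = 44 days away, refused.
- Visit 4 window, Day 26 to 30: Days 26 and 27 are 30 and 29 days away, refused; Days 28 to 30 are 28 to 26 days away, accepted.

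A subject whose only post-dose full Mayo is refused stays in mITT. SAP 7.2 and 7.3 code anything that is not a success as failure, which can be read to cover response, remission and mucosal healing. No rule covers change in Mayo or change in UCEIS. The limit is measured from the subject's own Visit 7 date, which is undefined for someone who did not attend Visit 7.

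**5. Can response be known without endoscopy?** Response needs a fall of at least 3 points and at least 30%, plus the bleeding criterion. The highest responding Visit 7 total is T = 3, 4, 5, 6, 7, 7, 8 for screening totals 6 to 12. With partial total p and endoscopy unknown (0 to 3), the total lies between p and p + 3. If the bleeding criterion is met, p ≤ T − 3 is a response, p > T is not, and T − 2 to T is open. If it is not met, the subject is a non-responder.

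The 47 eligible screening profiles times 64 Visit 7 sub-score triples give 3008 combinations. The bleeding criterion is met in 1760, of which 840 (48%) are open. This counts combinations and is not a probability.

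**The case against.** **The SAP may set the details.** Protocol section 8 leaves full analysis details to the SAP. That stands for derivations. It does not explain replacing the entry rule of the primary set or dropping an imputation that 8.3.1.2 states without condition. Only the further supportive MI in 8.3.4 is left to judgement.

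**Few subjects, if any, are affected.** Endoscopy is scheduled at Visit 7 and at early discontinuation (protocol 5.4 and Appendix A). This stands and limits the weight of the point. Endoscopy at discontinuation is not assured, though, because protocol 5.4 puts subject safety and well-being first in data collection at that visit.

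**The ±4-week limit may be sensible.** It stops a Day 14 score from standing in for Day 56. That is a fair reason to keep it, but the SAP does not give it and does not complete the rule.

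**The trial is exploratory.** The primary analysis is descriptive and there is no power calculation. That lowers the consequence but does not remove the selection.

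**Stronger readings that the documents do not support.** A reader might infer that out-of-window subjects have no handling at all; the failure category in SAP 7.2 and 7.3 can cover the binary endpoints. A reader might also infer that observed Visit 7 sub-scores make most missing endoscopies harmless. Only 840 of all 3008 combinations (28%) are open, but 3008 − 1760 = 1248 of the settled ones are settled by failing the bleeding criterion. Where it is met, about half stay open, and a subject who left before Visit 7 has no Visit 7 sub-scores.

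**Conclusion.** The contradiction between SAP 6.2.1 and protocol 8.3.1.2 is certain on entry, MI and the carry limit, and it is unexplained. Its consequence is conditional. It reaches the primary, secondary and covariate efficacy analyses, but only for dosed subjects with partial scores and no post-dose endoscopy. Each such subject leaves 3.6 points (active) or 7.1 points (placebo) of the response proportion undetermined, assuming the full 42 are randomized 28:14. If there are none, this exclusion changes no result.

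The loss of observed partial Mayo scores from their own endpoint is the hardest part to defend. A reader might infer that the SAP rule favours bertilimumab; the documents do not support a direction. The point should be fixed, but it does not undermine the trial.

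**What to change.** In SAP 6.2.1:

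- **(a) Entry.** Admit dosed randomized subjects with a screening full Mayo and either a partial Mayo from Visit 3 onward or any post-dose full Mayo. Neither document's subjects are then lost on score availability.
- **(b) Partial Mayo.** Analyse change in partial Mayo on all observed partial scores in that set.
- **(c) MI.** Restore the protocol's MI for Visit 7 Mayo and UCEIS when no observed or carried score exists. Say how the interval in 9.4.1 is formed, since an exact binomial interval needs whole counts. Say also how the bleeding criterion, remission and mucosal healing are obtained if only the total is imputed. Imputing sub-scores is optional: neither document specifies it, and it may be unstable with at most 42 subjects.
- **(d) Sensitivity analysis.** Replace the open-ended sentence with a named missing-as-failure analysis of response. It should cover all dosed randomized subjects without a Visit 7 outcome, including those still outside mITT under (a), except where observed Visit 7 sub-scores already determine response.
- **(e) Carry limit.** Reconcile it with the protocol. If it is kept, anchor it on planned Day 56 for subjects without Visit 7, and state how scores outside it are handled for binary and for continuous endpoints.
- **(f) Reason.** Explain any departure from protocol 8.3.1.2 that remains.

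The cost is SAP text, an MI step and a few tables, with no new visits or data. Intervals may be slightly wider. If the full MI model does not converge, the protocol's footnotes already allow a reduced one.
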